**Non-ACT (Not interventional)**

**1. METHODS**

**1.1. Study design**

This study is a single-center, prospective, observational cohort study conducted at a university hospital between February 9, 2023, and February 1, 2024. This study was conducted in conformity with the principles and regulations of the Helsinki Declaration and it was approved by the Institutional Ethics Committee with decision number 58, dated 09.02.2023. Informed consent was obtained from the parents prior to inclusion in the study.

**1.2. Patient Enrollment and Group Formation**

The inclusion criteria were as follows: (1) parents agreed to participate in the study (2) infants born in our hospital, who were followed up in the NICU, with a gestational age of <34 weeks and a birth weight of 1000-2000 grams. Infants who indicated UVC placement, and for whom NIRS measurements were taken both before and after UVC placement were included in the UVC (+) Study Group. Infants who did not have a UVC but matched the Study Group regarding gestational age and birth weight constituted the UVC (-) Control Group.

Infants who died during the first week of life, were transferred to another hospital, had chromosomal anomalies, major congenital anomalies affecting splanchnic bed monitoring (such as congenital heart disease, abdominal wall defects, or congenital diaphragmatic hernia), inherited metabolic disorders, hydrops fetalis, TORCH infections, multiple organ failure, spontaneous intestinal perforation, lesions in the area where the NIRS sensor was placed, or

whose UVC was removed for any reason before 24 hours, as well as those with severe anemia or polycythemia, were excluded from the study. Infants with a birth hemoglobin (Hb) level of 10 g/dl or below were considered severely anemic, and those with a Hb level of 22 g/dl or above were considered polycythemic.

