## 2.5. Data collection

**(a) Demographics and clinical data:** Maternal obstetric diseases (hypertension, diabetes, premature membrane rupture, chorioamnionitis), and prenatal steroid administration were all included in the prenatal data. The following natal data were recorded: gestational age (GA), gender, birth weight, presence of small for gestational age (SGA), mode of delivery, 5th minute Apgar score, and need for resuscitation at birth, cord blood gas parameters (pH, HCO3, BE, lactate) and initial hemoglobin value. Gestational age was determined by asking about the last menstrual period and performing an ultrasonographic examination. According to Fenton et al. (7), SGA is defined as a birth weight less than the 10th percentile. Nutritional measurements including the time to first feeding, initial feeding type (breast milk, formula or mixed), time to reach full enteral feeding (FEF:120 ml/kg/day), and the presence of delayed passage of the first meconium (> 48 h) were recorded.

Clinical gastrointestinal and/or radiological findings observed during hospitalization were noted as vomiting, gastric residue (residual gastric volume exceeding 50% of the previous

feeding volume), abdominal distension, prominent bowel loops, occult or overt blood in the stool, bowel dilation, pneumatosis intestinalis, portal venous gas, and the presence of pneumoperitoneum in the abdominal radiography. These findings were evaluated both between the groups and within the UVC (+) group, comparing the periods when the catheter was in place and after its removal.

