Postnatal morbidities such as respiratory distress syndrome (RDS), hemodynamic significant patent ductus arteriosus (HsPDA), grade 2-3 intraventricular hemorrhage (IVH), FI, NEC, and sepsis were noted. Gastric residual volume of more than 50% of the previous feeding volume, emesis, abdominal distention, or both, and a reduction, delay, or cessation of enteral feedings were the criteria used to define feeding intolerance (8). According to the modified Bell's criteria (9), stage II/III NEC was used as an outcome parameter. Echocardiography was used to determine the presence of HsPDA. Positive blood culture was used to define proven sepsis. The Papile classification system was used to classify IVH (10). Furthermore, the need for inotropic support during the first week of life, parenteral nutrition durations, invasive/non-invasive mechanical ventilation support, total respiratory support, oxygen support, hospitalization, and mortality were recorded.

**(b) Splanchnic near-infrared spectroscopy (NIRS) monitoring:** As soon as the infants were admitted to the NICU on the first day of life (DOL), a self-adhesive transducer (cerebral/somatic-neonatal NIRSensor) with a light-emitting diode and two remote sensors was applied to the infra-umbilical abdominal region to continuously record regional splanchnic saturation (rSO2S). Continuous rSO2S monitoring was carried out for 1 week using NIRS (INVOS 5100; Covidien Somanetics, Troy, MI), simultaneously together with continuous preductal oxygen arterial saturation (SaO2) monitoring using a pulse oximetry device (Nellcor, Covidien-Medtronic, Minneapolis, MN) with a target band of 90–95% and alarm settings of 89 and 96% in the case of oxygen therapy. Based on the simultaneous measurements of rSO2S and

$\text{SaO}_2$ , the infants' fractional tissue oxygen extractions ( $\text{FOE} = \text{SaO}_2 - \text{rSO}_2\text{S} / \text{SaO}_2$ ), which represent the balance between oxygen delivery and oxygen consumption, were assessed. After removing artifacts that may indicate sensor misplacement,  $\text{SaO}_2$  and NIRS parameters ( $\text{rSO}_2\text{S}$ ,  $\text{FOE}$ ) were calculated as means on each day of the first week of life (WOL).

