Infants with an UVC were included in the UVC (+) Study Group, while those without a catheter were included in the UVC (-) Control Group. Continuous measurements taken during the first WOL were compared both between the groups and within each group on a day-to-day basis. Splanchnic NIRS monitoring was terminated 24 hours after the removal of the UVC. In the UVC (+) Group, the day and time of catheter placement and removal were recorded. Splanchnic oxygenation measurements were compared at the following time intervals: one hour before UVC placement, one hour after UVC placement, 24 hours before UVC removal, and 24 hours after UVC removal. Additionally, the daily means in the UVC (+) Group during the period when the UVC was in place were compared with the daily means in the UVC (-) Group. Clinical parameters and splanchnic NIRS data were compared between the UVC (+) and UVC (-) Groups. The birth hemoglobin (Hb) value of the UVC (+) Group, as well as the Hb value on the day the UVC was removed, were recorded, and a repeated measures analysis was performed.

The primary outcomes included comparing continuously recorded  $\text{rSO}_2\text{S}$  and  $\text{FOE}$  values during the first WOL between the UVC (+) and UVC (-) groups, assessing  $\text{rSO}_2\text{S}$  and  $\text{FOE}$  measurements within the UVC (+) Group before and after UVC placement and removal, and determining the impact of UVC on splanchnic oxygenation. The secondary outcomes involve evaluating the relationship between UVC presence and the incidence of feeding intolerance and necrotizing enterocolitis.

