### **1.5.2. Statistical analysis**

The statistical data were analyzed using IBM SPSS 21.0 software (IBM Corp. Released 2012. IBM SPSS Statistics for Windows, Version 21.0. Armonk, NY: IBM Corp.). The normality of variable distribution was assessed by Shapiro-Wilk test. The data were presented as a mean±standard deviation (SD), median (Q1–Q3), frequency, and percentage. For comparing normally distributed groups with two groups, the independent samples t-test was used. For comparing non-normally distributed groups with two groups, the Mann-Whitney U test was used. For comparing values at different time points, the Wilcoxon test was used when there were two groups, and the Friedman test was used when there were three or more groups. For repeated measurements, the two-way repeated measures ANOVA (One Factor Repetition) test was used. To determine the direction and magnitude of the relationship (correlation) between variables, Pearson correlation coefficients were calculated for normally distributed variables, and Spearman correlation coefficients were calculated for non-normally distributed variables. For the analysis of cross-tabulations, Pearson Chi-Square, Yates' Chi-Square, and Pearson Exact Chi-Square tests were used. The McNemar-Bowker test was used for comparing categorical clinical findings at two different time points. Covariance analysis was used to assess the importance of the model that had been installed with the confounding factors. A p-value of <0.05 was considered the criterion for statistical significance.

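### Catheter infants are chosen by clinical indication, and the plan does not tie the primary between-group comparison to any specified adjustment for early illness or pre-catheter NIRS

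*Combined protocol and SAP*

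**What the plan says.** Section 1.1 describes a "single-center, prospective, observational cohort study", so the catheter is not randomised. Section 1.2 defines the groups:

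- Exposed: "Infants who indicated UVC placement", provided that NIRS was recorded on both sides of the placement.
- Control: "Infants who did not have a UVC but matched the Study Group regarding gestational age and birth weight constituted the UVC (-) Control Group".

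No measure of illness enters the matching. The same section excludes several severe conditions, among them death in the first week, multiple organ failure and severe anaemia.

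The primary outcomes, at the end of section 2.5(b), are the first-week group comparison of rSO2S and FOE, the comparisons within catheter infants around placement and removal, and "determining the impact of UVC on splanchnic oxygenation".

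Section 1.5.2 lists the t-test or Mann-Whitney test for two groups and a two-way repeated measures ANOVA, with no covariates named for any of them. It also states: "Covariance analysis was used to assess the importance of the model that had been installed with the confounding factors".

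Section 2.5(a) records "5th minute Apgar score, and need for resuscitation at birth, cord blood gas parameters" and initial haemoglobin. Section 2.5(b) starts NIRS at NICU admission on the first day of life and uses the hour before placement in the catheter group's time comparisons.

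**The concern.** An infant judged to need central access may already differ in splanchnic perfusion from one of the same gestation and weight who does not. Matching on gestation and weight leaves that difference in place. A t-test or repeated measures ANOVA on group alone would then credit it to the catheter, although the stated aim is to determine the catheter's impact.

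The one sentence on adjustment does not settle the matter. It does not say which variables are confounders, which outcome the model is for, or whether the adjusted or the unadjusted result carries the conclusion. As worded, it would allow covariates to be chosen after the results are seen. It would also allow adjustment for events after placement, such as "the need for inotropic support during the first week of life", which may lie on the path from catheter to outcome. The most useful covariate, the infant's own NIRS value before any catheter, can be drawn from the recording but is nowhere used as one.

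**Working it through.** **1. The plan's own figure.** Section 1.5.1 gives 21 per group for alpha 0.05, effect size d = 0.8 and 80% power, without stating sidedness. With the noncentral t distribution:

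- one-sided: n = 20.03, rounded up to 21, with power 0.817 at 21;
- two-sided: n = 25.52, rounded up to 26, with power 0.716 at 21.

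The figure reproduces only as a one-sided t-test. The present point does not depend on this. The two-sided power of 0.716 is the unadjusted reference below.

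**2. What is and is not specified.**

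| Element | In the plan |
|---|---|
| Assignment | Clinical indication (1.2) |
| Matching | Gestational age, birth weight (1.2) |
| Listed group tests | t-test/Mann-Whitney, repeated measures ANOVA; no covariates (1.5.2) |
| Covariance analysis | Mentioned; covariates, outcome and status not given (1.5.2) |
| Pre-catheter NIRS | Time-interval comparison only (2.5(b)) |

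**3. Possible size of the bias (assumptions).** The documents give neither an illness imbalance nor its correlation with rSO2S. Assume a severity difference of 0.5 to 1.0 SD and a correlation of 0.3 to 0.5.

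Bias = severity difference × correlation, so 0.5 × 0.3 = 0.15 SD up to 1.0 × 0.5 = 0.50 SD.

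Two-sided rejection rate with no catheter effect and 21 per group (noncentral t, noncentrality = bias × √(21/2)):

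| Bias (SD) | Rejection rate |
|---|---|
| 0 | 5% |
| 0.15 | 7.6% |
| 0.25 | 12.4% |
| 0.30 | 15.8% |
| 0.40 | 24.4% |
| 0.50 | 35.3% |

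**4. Effect of adjusting for early NIRS on precision (assumptions).** With baseline-outcome correlation ρ and baseline imbalance D in SD units, the standard error is multiplied by about √(1 − ρ²) × √(1 + D²/4). Power at d = 0.8 is that of a t-test with effect 0.8 divided by this factor:

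| ρ | D | SE factor | Power at 21 per group |
|---|---|---|---|
| unadjusted | – | 1.000 | 0.716 |
| 0.5 | 0 | 0.866 | 0.832 |
| 0.5 | 0.5 | 0.893 | 0.809 |
| 0.5 | 1.0 | 0.968 | 0.743 |
| 0.6 | 0 | 0.800 | 0.885 |
| 0.6 | 0.5 | 0.825 | 0.866 |
| 0.6 | 1.0 | 0.894 | 0.807 |

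The confounding argument presumes imbalance, so the D = 0 rows are a best case.

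**5. Bias left after adjusting for early NIRS alone (assumptions).** Suppose illness shifts the early value and the later mean by the same 0.5 SD. The remaining bias is 0.5 × (1 − ρ), which is 0.25 SD at ρ = 0.5 and 0.20 SD at ρ = 0.6. Dividing by the D = 0.5 factors gives 0.25/0.893 = 0.280 and 0.20/0.825 = 0.243. The corresponding rejection rates are about 14% and 12%, down from 35% but still above 5%.

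**The case against.** A reader might infer that the group comparison is simply unadjusted, or that the covariance analysis is an afterthought with no bearing on the conclusion. The documents do not support either reading. Section 1.5.2 says that a covariance analysis with confounding factors was used, and no section ranks the tests or says which one carries the conclusion. What can be said is that the adjustment is unspecified.

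Three further points count in the plan's favour.

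- **Within-infant comparisons are also primary.** Comparing the same infant before and after placement and removal cancels fixed differences between infants, and the aim about impact does not rest on the group comparison alone. These comparisons do not remove postnatal time trends or the effect of concurrent treatment, and they do not repair the between-group result.
- **The exclusions narrow the range of severity.** They do not balance it between the groups.
- **The indication need not be sickness.** The documents do not state the indications for a catheter. Parenteral nutrition is started in very low birth weight infants and in those with insufficient enteral intake (section 1.3), so the indication may be partly nutritional or related to size, and birth weight is matched. It would go too far to say that the catheter infants are shown to be sicker or that an observed difference would be spurious. The severity gap used above is an assumption.

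There is also a practical objection. Section 1.1 gives study dates ending in February 2024 and the methods are in the past tense, so naming a main model now may be post hoc. Section 2.5(b) describes daily means, and controls have no placement time, so an hourly control baseline needs fresh extraction. Both points stand and are reflected in the fix.

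**Conclusion.** The concern holds in a limited form. Assignment by indication, with matching on two variables only, leaves the between-group rSO2S and FOE comparison open to confounding. The plan mentions adjustment but does not commit that comparison to a defined adjusted model or use the pre-catheter NIRS value in one.

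The size is illustrative, since the documents supply no imbalance or correlation. An illness-driven shift of 0.15 to 0.50 SD would raise the two-sided false-positive rate at 21 per group from 5% to about 8% to 35%. Adjusting for early NIRS at ρ of 0.5 to 0.6 would lift power at d = 0.8 from 0.72 to between 0.83 and 0.89 with balanced baselines, but only to between 0.74 and 0.81 at a 1.0 SD baseline imbalance. Because some bias may remain, an adjusted result still supports a statement of association and not of causal impact.

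**What to change.** Specify the covariance analysis already mentioned, or an equivalent mixed model for the daily means, as the main between-group analysis of rSO2S and FOE:

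- **Baseline NIRS:** in catheter infants, the hour before placement; in controls, the hour at matched postnatal age from the continuous recording, with a written alignment rule.
- **Other covariates:** gestational age and birth weight (which also keeps the matching in the analysis), and at most one or two severity variables that precede placement, for example cord pH or lactate, or 5-minute Apgar.
- **Not adjusted for:** variables that arise after placement, such as sepsis, HsPDA, inotropic support or duration of ventilation.
- **Reporting:** unadjusted tests as supportive, the adjusted model labelled post hoc if the data have already been analysed, and the between-group finding worded as an association.

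The cost is some analysis time and new wording, plus extraction of an hourly baseline for controls. That hour may be missing where recording began too late. No new measurements on infants are needed. With about 42 infants (2 × 21) the covariate list must stay at four or five.

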## **1.5. Data analysis**

### **1.5.1. Sample size**

A power analysis was performed prior to the study using the summary values from our previous study, 'The Effect of Drip Versus Intermittent Feeding On Splanchnic Oxygenation In Preterm Infants With Intrauterine Growth Restriction: A Prospective Randomized Trial' (6). A sample size of at least 21 infants per group (UVC (+) versus UVC (-) group) was estimated to obtain statistically significant results with a Type-1 error rate of 0.05 (95% confidence level), an effect size of 0.8 (high), and 80% power.

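### Controls are matched on gestational age and birth weight, but the plan does not secure either factor in the primary between-group comparison, so precision may be forgone

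*Combined protocol and SAP*

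**What the plan says.** **Control selection (1.2).** The control group consists of infants without a catheter who "matched the Study Group regarding gestational age and birth weight". No ratio, caliper, algorithm or pair identity is given. Eligibility is limited to infants "with a gestational age of <34 weeks and a birth weight of 1000-2000 grams".

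**Primary outcome (2.5).** One of the primary comparisons is of rSO2S and FOE "values during the first WOL between the UVC (+) and UVC (-) groups".

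**Tests (1.5.2).** "For comparing normally distributed groups with two groups, the independent samples t-test was used". Where normality fails, the Mann-Whitney test takes its place and is likewise unpaired. Repeated values are handled as follows: "the two-way repeated measures ANOVA (One Factor Repetition) test was used"; no matched-set term or covariate is mentioned. The Wilcoxon and McNemar-Bowker tests are assigned to different time points, not to matched infants. One further sentence refers to a covariance analysis with confounding factors. It does not list them, name an outcome, or say whether the analysis is primary.

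**Sample size (1.5.1).** "A sample size of at least 21 infants per group", from an effect size of 0.8, a type I error of 0.05 and 80% power. Matching is not mentioned.

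**The concern.** Matching on prognostic factors makes the group means more alike on those factors, which reduces the real sampling variance of the group difference. An unpaired test still puts the variance explained by those factors into its error term. So far as the matching works and the factors predict the outcome, the reported standard error is too large, the interval too wide and the test conservative.

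Conservatism is not harmless here. The question is whether a catheter impairs splanchnic oxygenation, and a missed effect could be read as reassurance. Because no caliper is stated, some imbalance in gestational age or birth weight may also remain, and the unpaired tests cannot correct it.

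**Working it through.** **Inputs.** From 1.5.1: n = 21 per group, d = 0.8, alpha 0.05. Sidedness is not stated. Assumed: r, the share of outcome variance explained by gestational age and birth weight together, 0 to 0.4.

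**1. The plan's own figure.** For an unpaired t-test the noncentrality is d·√(n/2) = 0.8·√10.5 = 2.592 on 40 degrees of freedom.
- One-sided: 21 is the smallest n reaching 80%, with power 81.7%.
- Two-sided: 21 per group gives 71.6%, and 26 are needed.

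So 21 reproduces as a one-sided, unpaired calculation. The figures below are two-sided unless stated.

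**2. Power.** For a model with group and two covariates, balanced between groups, the noncentrality is 2.592/√(1−r) on 38 degrees of freedom. It is 2.73 at r = 0.1, 2.90 at 0.2, 3.10 at 0.3 and 3.35 at 0.4. Unadjusted power was simulated with the matching score shared exactly between groups.

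| r | Unadjusted | Adjusted | Difference, points |
|---|---|---|---|
| 0 | 72% | 71% | about −1 or less |
| 0.05 | 72% | 74% | +2 |
| 0.1 | 72% | 76% | +4 |
| 0.2 | 74% | 81% | +7 |
| 0.3 | 75% | 86% | +11 |
| 0.4 | 76% | 90% | +14 |

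Simulations with exact, stratified and loose matching gave gains of about 3 to 13 points for r = 0.1 to 0.4. Across these settings unadjusted power stays at about 71-77%.

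**3. Standard error and type I error.** Under exact matching the true variance of the difference is (1−r) times what the unpaired test estimates. The unpaired SE is then too large by the factor 1/√(1−r): 1.054, 1.118, 1.195 and 1.291 at r = 0.1, 0.2, 0.3 and 0.4. The simulated type I error at a nominal 5% depends on how the matching was done:
- near-exact matching: about 4% at r = 0.1, falling to 1.3% at r = 0.4;
- frequency matching in two strata: about 4.4% falling to 2.4%;
- very loose matching (same distribution only): about 5% throughout.

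**4. If pairs exist.** A paired t-test on 21 pairs, with within-pair correlation equal to r, has power of 69%, 74%, 79% and 84% at 0, 0.1, 0.2 and 0.3. That is slightly below the covariate model at each value, and below the unpaired test when the correlation is zero.

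**The case against.** - **The factors may already be adjusted for.** The covariance analysis is the same kind of model as the remedy, and gestational age and birth weight are the obvious candidates for it. This stands against the stronger reading that the plan ignores both factors: the documents neither confirm nor exclude their inclusion. It does not answer the narrower point, because that sentence does not commit the primary comparison to adjustment.
- **The t-test may not be the primary test.** Section 1.5.2 is a generic list, and daily values over a week may go to the repeated-measures ANOVA. This is fair, and the power figures, which are for a single summary value, are then only indicative. The ANOVA as described has no matching term either.
- **The size of the SE error is unknown.** A reader might infer that the error bars are wrong and the true type I error is near 1%. That needs near-exact matching and a high r, and the documents give neither. Enrolment limits also narrow the spread of both factors.
- **No power is lost in absolute terms.** Correct: unpaired power does not fall below its unmatched value of about 72%. On the one-sided reading that reproduces 21, it is 82-86% for r from 0 to 0.3, above target. The tightness of the sample is a separate matter.
- **The error is conservative and secondary to confounding by indication.** Adjusting for two covariates will not remove differences between infants with and without a catheter indication. That limits the importance of the point but is no reason to leave out a nearly free improvement.

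**Conclusion.** The concern holds in a limited form. The design uses gestational age and birth weight, the named two-group tests do not, and the unspecified covariance analysis does not close the gap.

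The consequence is conditional. If r is about 0.2 to 0.3, adjustment gains roughly 7 to 11 points of two-sided power at d = 0.8; if r is near zero it gains nothing. These figures rest on an assumed r, a single outcome value per infant, a linear relation and 21 infants per group.

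A reader might also infer that a paired test is required. The documents do not support that, since one-to-one pairs are never described. Covariate adjustment works whichever form of matching was used, which makes it the safer recommendation. The change is worth making but does not by itself invalidate the planned comparison.

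**What to change.** 1. In 1.5.2, make the primary between-group comparison of rSO2S and FOE a linear mixed model, or an ANCOVA if a single summary value is used. Include group, day (for the mixed model), and gestational age and birth weight as named continuous covariates.
2. In 1.2, state how controls were matched: ratio, tolerance, and whether individually or by group. Add a matched-pair random effect only if controls were chosen one-for-one.
3. Keep the unpaired t-test and Mann-Whitney results as descriptive.
4. State the role of the existing covariance analysis: either it is this model, or it is a separate sensitivity analysis with its covariates listed.

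**Cost.** A few lines of SAP text and analysis code; section 2.5 already records both variables. Two degrees of freedom are used (40 to 38), and about one point of power or less is lost if r = 0 and the matching has balanced the covariates.

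### The transfer exclusion has no time limit and covers the whole study, so a transfer after NIRS monitoring has ended discards complete primary data and any FI or NEC event already diagnosed

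*Combined protocol and SAP*

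**What the plan says.** Section 1.2 gives the exclusions as one long sentence. It opens with "Infants who died during the first week of life, were transferred to another hospital, had chromosomal anomalies", continues through a series of diagnoses and early catheter removal, and ends "as well as those with severe anemia or polycythemia, were excluded from the study". The time limit sits with death. Catheter removal has its own limit (24 hours). Transfer has none, and no reason for transfer is specified.

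Section 2.5 sets the measurement windows:

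- **NIRS.** "Continuous rSO 2 S monitoring was carried out for 1 week using NIRS", and SaO2, rSO2S and FOE "were calculated as means on each day of the first week of life (WOL". NIRS recording ends 24 hours after the UVC is removed, and one of the planned contrasts uses those 24 hours.
- **Gut findings.** "Clinical gastrointestinal and/or radiological findings observed during hospitalization were noted as vomiting" and other signs, so collection runs through the hospital stay.
- **NEC.** "stage II/III NEC was used as an outcome parameter", with no time window.
- **Secondary outcomes.** "The secondary outcomes involve evaluating the relationship between UVC presence and the incidence of feeding intolerance and necrotizing enterocolitis".

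No section keeps the earlier data of a transferred infant, provides follow-up after transfer, or states how many transfers are expected.

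**The concern.** An exclusion should match the period in which the outcome is measured. Here the primary outcomes are finished early in the stay, while the transfer rule runs to the end of it. An infant moved in week 3 can have every primary measurement in hand and still be removed.

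Transfer also happens after exposure and may depend on how the infant is doing: a recovering infant may be sent closer to home, and one with a complication may be sent elsewhere. Removing infants on that basis makes both groups conditional on later course. UVC (+) and UVC (-) infants may differ in illness severity, so the losses need not balance.

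For the secondary outcomes, an infant whose FI or NEC was diagnosed in this unit and who was then transferred leaves both numerator and denominator, although the event was observed.

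**Working it through.** **1. Which items carry the first-week limit.** The limit directly follows the verb for death. Most later items in the sentence, such as chromosomal anomalies and inherited metabolic disorders, cannot carry it, so it does not run across the list. Where a second limit was wanted, for catheter removal, it was written out. On its wording, transfer is unlimited.

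**2. When the primary data are complete.**

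- Daily means for the between-group comparison: end of day 7 (section 2.5).
- Removal contrast: 24 hours after removal (section 2.5).
- Recommended maximum UVC duration: 7-10 days (section 1.4).
- Assuming placement on about the first day of life and removal within that maximum, the latest completion is 10 + 1 = about day 11.

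A transfer after that point costs the primary comparison a complete record. A transfer before it leaves an incomplete one whatever the rule says. The point about discarded complete data therefore concerns later transfers only.

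**3. What happens to FI and NEC.** Gut findings are collected through the hospital stay and NEC has no window, so an event can be diagnosed here before a transfer. Exclusion from the whole study then deletes it.

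**4. The plan's sample size, and what a loss would mean.** Section 1.5.1 states: "A sample size of at least 21 infants per group (UVC (+) versus UVC (-) group) was estimated", with type 1 error 0.05, effect size 0.8 and 80% power. A two-sample t-test gives:

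- one-sided: n = 20.03, rounded up to 21, which reproduces the plan;
- two-sided: n = 25.52, rounded up to 26, which does not.

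The plan does not state the number of sides. That is a separate matter, so the one-sided setting is used here. If infants were lost from 21 per group and not replaced, power would be:

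| n per group | One-sided power at d = 0.8 |
|---|---|
| 21 | 81.7% |
| 20 | 79.9% |
| 19 | 78.1% |
| 18 | 76.0% |

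This is conditional on no replacement, which the plan does not say.

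**5. NEC under assumed rates.** The documents give neither a NEC rate nor a transfer rate. All rates below are assumptions.

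- *Transfer unrelated to NEC.* Expected cases removed per group = 21 × NEC rate × transfer rate. With NEC 5% and transfer 5% to 15%: 21 × 0.05 × 0.05 = 0.05, up to 21 × 0.05 × 0.15 = 0.16.
- *Transfer tied to NEC.* Let r be the true rate and s the share of NEC infants transferred, with no other infant transferred. Observed rate = r(1 − s)/(1 − rs).

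| r | s | Observed rate | NEC cases removed of 42 infants (42rs) |
|---|---|---|---|
| 5% | 25% | 3.8% | 0.5 |
| 5% | 50% | 2.6% | 1.05 |
| 10% | 25% | 7.7% | 1.05 |
| 10% | 50% | 5.3% | 2.1 |

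The effect runs from negligible to a halving of the observed rate. The documents do not say where in that range this unit lies.

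**The case against.** **The first-week limit may be shared.** Death and transfer open the list as the two events that end care in the unit, and a common first-week window would fit one week of monitoring. This reading is possible. If it was meant, most of the loss of complete primary data disappears, because an infant leaving in week 1 has an incomplete series anyway. The sentence does not say it, however, and the text would still need correcting.

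**Power.** A reader might infer that the rule leaves the study underpowered. The documents do not support this. The target is a minimum, and nothing says that excluded infants come out of the 21 without replacement. Replacement would restore the numbers, though not remove the selection.

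**NEC.** A reader might also infer that the NEC count is seriously depleted, since at a 5% rate only 21 × 0.05 = 1.05 cases per group are expected and one deletion could empty a group. That is a worst case: the expected case must also be the one transferred. The study takes place in a university hospital and enrols infants born there, and no section describes sending gut complications elsewhere.

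**Fit with the analysis.** Censoring at transfer would need a time-to-event method, and section 1.5.2 plans only chi-square-type tests for between-group categorical outcomes. The repeated-measures ANOVA and Friedman test normally need complete series, so early transfers would drop out regardless. Both points stand and shape the fix.

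**A single population.** Excluding transfers gives one fully followed set for time to full feeding, support durations and length of stay. That is a fair reason to leave them out of discharge-dependent outcomes, but not out of outcomes already measured.

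**Conclusion.** The concern holds on the wording. The rule excludes a transferred infant from the whole study at any time, and no other section limits it or keeps that infant's data. A transfer after monitoring has ended discards a complete primary record, deletes any FI or stage II/III NEC already diagnosed, and selects both groups on a post-exposure event.

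The size is unknown and could be nil if the unit seldom transfers infants. The documents do not show that any infant was lost this way, that transfer was linked to gut complications, or that power fell. The power and NEC figures above are illustrations under assumed rates. The conclusion rests on the literal reading of section 1.2. It still calls for a change, because matching the analysis set to each outcome reduces selection at little cost.

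**What to change.** 1. In section 1.2, limit the transfer exclusion to transfers before NIRS monitoring is complete.
2. Keep infants transferred later in the between-group NIRS comparisons and in the placement and removal contrasts.
3. Count FI and NEC diagnosed before transfer in the between-group tests already planned in section 1.5.2. Add a sensitivity analysis that leaves out transferred infants without an event, to show how far the result depends on treating them as event-free.
4. Leave transferred infants out only of discharge-dependent durations, such as length of hospital stay.
5. Report transfers by group, with timing, reason and FI/NEC status at transfer.

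**Cost.** A short change to the eligibility text, a definition of the analysis set for each outcome, and one sensitivity analysis; no new statistical method is needed. FI/NEC follow-up will be shorter for a few infants, and denominators will differ slightly across outcomes. The stated study period has ended, and the documents do not say whether data on excluded infants were kept. If they were not, items 2 and 3 cannot be carried out for those infants, and the report should say so and give as much of item 5 as is available.
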